4.5.2 Nivolumab Toxicity Management

Table 4.6: Nivolumab related toxicity management guidelines		
Immune-Mediated Reactions		
Immune-related Adverse Events (Overall Management)		
Drug administration modifications of study drug/study regimen will be made to manage potential immune-related AEs based on severity of treatment- emergent toxicities graded per NCI CTCAE v4.03.		
Grade	Dose Modifications	Toxicity Management
Grade 1	Continue dosing	It is recommended that management of irAEs follow the guidelines presented in this table and refer to the nivolumab investigator brochure 
 
Subjects should be thoroughly evaluated to rule out any alternative etiology (e.g., disease progression, concomitant medications, infections, etc.)
Grade 2	Hold study drug up to 28 days until resolution to ≤ Grade 1 or baseline 
 
If toxicity worsens 	

	
then treat as Grade 3 or Grade 4
 
 If toxicity improves then treat at next scheduled treatment date 	
 In the absence of a clear alternative etiology, all events should be considered potentially immune related. Symptomatic and topical therapy should be considered for low-grade (Grade 1 or 2, unless otherwise specified) events Systemic corticosteroids (e.g., prednisone or IV equivalent) should be considered for persistent low-grade or severe (Grade ≥3) events If symptoms recur or worsen during corticosteroid tapering, increase the corticosteroid dose until stabilization or improvement of symptoms, then resume corticosteroid tapering at a slower rate More potent immunosuppressives – TNF antagonist class (e.g., infliximab) or mycophenolate, etc.) should be considered for events not responding to systemic steroids after discussion with study physician
Grade 3	Depending on the individual toxicity, may permanently discontinue study drug/study regimen. Please refer to guidelines below	
Grade 4	Permanently discontinue study drug/study regimen	
 Discontinuation of study drug is not mandated for Grade3 / Grade4 inflammatory reactions attributed to local tumour response (e.g. inflammatory reaction at sites of metastatic disease, lymph nodes etc.)
Pneumonitis/ILD		
*See section 7.2.5 for a description of AESI's (Adverse Events of Special Interest). Such AESI's should be monitored carefully and discussed with the treating physician (PI or sub-I) to determine attribution.		
Grade	Dose Modifications	Toxicity Management
Any Grade		
 Monitor subjects for signs and symptoms of pneumonitis or ILD (new onset or worsening shortness of breath or cough). Subjects should be evaluated with imaging and pulmonary function tests including other diagnostic procedures as described below Initial work-up may include clinical evaluation, monitoring of oxygenation via pulse oximetry (resting and exertion), laboratory work-up and high-resolution CT scan.
Grade 1	No dose hold required. However, consider holding study drug/study regimen dosing as clinically appropriate and during diagnostic work-up for other etiologies.	
For Grade 1 (Radiographic Changes Only)
 
 Monitor and closely follow up in 2-3 days for clinical symptoms, pulse oximetry (resting and exertion) and laboratory work- up and then as clinically indicated Consider pulmonary and infectious disease consult Re-image at least every 3 weeks
Grade 2	
Hold study drug up to 28 days until resolution to ≤ Grade 1 or baseline:
 
 If toxicity worsens then treat as Grade 3 or Grade 4 If toxicity improves then treat at next scheduled treatment date 	
For Grade 2 (Mild to Moderate New Symptoms)
 
 Monitor symptoms daily and consider hospitalization Discuss with study physician and consider systemic steroids (e.g., prednisone 1- 2mg/kg/day or IV equivalent) Reimaging as clinically indicated If no improvement within 3-5 days, additional workup and treatment with IV methylprednisolone 1mg/kg/day should be considered If no improvement within 3-5 days, further immunosuppressive therapy (e.g., infliximab) should be considered. Once improving, gradually taper steroids over ≥4 weeks and consider prophylactic antibiotics Consider pulmonary and infectious disease consult
Grade 3 or 4	Permanently discontinue study drug/study regimen	
For Grade 3 or 4 (severe or new symptoms, new/worsening hypoxia, life threatening)
 
 Discuss with study physician pulmonary and infectious disease consult

		
 • Hospitalize the patient • Supportive Care (oxygen, etc.) • Initiate empiric IV corticosteroids (e.g., methylprednisolone or equivalent) at 1 to 2 mg/kg/day • If no improvement within 3-5 days, additional workup and treatment with additional immunosuppressive therapy (e.g., infliximab) should be considered • Once improving, gradually taper steroids over ≥6 weeks and consider prophylactic antibiotics
Diarrhea/ Enterocolitis		
Grade	Dose Modifications	Toxicity Management
Any Grade		
 • Monitor for symptoms that may be related to diarrhea/enterocolitis (abdominal pain, cramping, or changes in bowel habits) • Subjects should be thoroughly evaluated to rule out any alternative etiology (e.g., disease progression, infections, etc.) • Steroids should be considered if an alternative etiology is not determined, even for low grade events, in order to prevent potential progression to higher grade event • Use analgesics carefully; they can mask symptoms of perforation and peritonitis
Grade 1	Continue dosing	
 • Close monitoring for worsening symptoms • Consider symptomatic treatment including hydration, electrolyte replacement, dietary changes (e.g., American Dietetic Association colitis diet), and loperamide
Grade 2	Hold study drug up to 28 days until resolution to ≤ Grade 1 or baseline 
 • If toxicity worsens then treat as Grade 3 or Grade 4 • If toxicity improves then treat at next scheduled treatment date 	
 • Consider symptomatic treatment including hydration, electrolyte replacement, dietary changes (e.g., American Dietetic Association colitis diet), and loperamide and/or budesonide • Rule out infectious etiologies prior to steroid initiation: 
 ○ If event is persistent (> 3-5 days) or worsens, consider prednisone 0.5 to 1 mg/kg/day or IV equivalent ○ If not responsive within 3-5 days, consider IV corticosteroids (e.g., methylprednisolone IV or equivalent) at 0.5-1.0 mg/kg/day ○ If event is not responsive within 3-5 days or worsens, additional workup and treatment with IV methylprednisolone 1-2mg/kg/day should be considered • If no improvement within 3-5 days, further immunosuppressives (e.g., infliximab) should be considered • Consult study physician if no resolution to ≤ Grade 1 in 3-4 days • Once improving, gradually taper steroids over ≥4 weeks
Grade 3 or 4	Permanently discontinue study drug/study regimen	
 • Discuss with study physician • Monitor stool frequency and volume and maintain hydration • Urgent GI consult and imaging as appropriate • Initiate empiric IV corticosteroids (e.g., methylprednisolone IV or equivalent) at 1 to 2 mg/kg/day • If no improvement within 3-5 days, consider further immunosuppressives (e.g., infliximab). • Caution: Ensure GI consult to rule out bowel perforation and refer to label before using infliximab. Once improving, gradually taper steroids over ≥4 weeks and consider prophylactic antibiotics

Hepatitis (Elevated LFTs)		
*See section for 7.2.5 for a description of AESI's, defined as any increase in ALT or AST to greater than 3 × ULN and concurrent increase in bilirubin to greater than 2 × ULN. Such AESI's should be monitored carefully and discussed with the treating physician (PI or sub-I) to determine attribution.		
Grade	Dose Modifications	Toxicity Management
Any Grade		
 Monitor and evaluate liver function test: AST, ALT, ALP and total bilirubin Evaluate for alternative etiologies (e.g., viral hepatitis, disease progression, concomitant medications)
Grade 1	Continue dosing. If it worsens, treat as Grade 2 event	
 Continue LFT monitoring per protocol
Grade 2*	Hold Study drug up to 28 days until resolution to ≤ Grade 1 or baseline 
 If toxicity worsens then treat as Grade 3 or Grade 4 If improves then treat at next scheduled treatment date 	
 Discuss with study physician if no resolution to ≤ Grade 1 in 1-2 days Recheck LFT's in 1 to 2 days. If event is persistent (> 3-5 days) or worsens, consider prednisone 0.5 to 1 mg/kg/day or IV equivalent. If no improvement within 3-5 days, consider additional workup and treatment with IV methylprednisolone 2-4mg/kg/day 
 If no improvement within 3-5 days after methylprednisolone, consider further immunosuppressives (e.g., mycophenolate mofetil) Once improving, gradually taper steroids over ≥4 weeks and consider prophylactic antibiotics
Grade 3 or higher	For elevations in transaminases ≥ 5 × ULN, or elevations in bilirubin ≥ 3 × ULN, permanently discontinue study drug/study regimen.	
 Discuss with the study physician Initiate empiric IV corticosteroids (e.g., methylprednisolone IV or equivalent) at 1 to 4 mg/kg/day 
 If no improvement within 3-5 days, consider further immunosuppressive therapy (e.g., mycophenolate mofetil) If still no further improvement within 3-5 days consider other immunosuppressive therapy per local guidelines Hepatology consult, abdominal workup, and imaging as appropriate. Once improving, gradually taper steroids over ≥4 weeks and consider prophylactic antibiotics
Immune-Mediated Nephritis and Renal Dysfunction		
Any Grade		
 Monitor and evaluate renal function tests (comprehensive chemistry panel) Evaluate for alternative etiologies
Grade 1	Continue dosing.	
 Continue comprehensive chemistry plan per protocol
Grade 2 or 3	Hold Study drug up to 28 days until resolution to ≤ Grade 1 or baseline 
 If toxicity worsens then treat as Grade 	
 Discuss with the study physician Consider empiric steroids at a dose of 0.5 to 1 mg/kg/day or IV equivalent. Consider renal biopsy with nephrology consult

	
3 or Grade 4
 
 If improves to baseline then treat at next scheduled treatment date 	
 Monitor creatinine every 2-3 days
Grade 4	Permanently discontinue study drug/study regimen	
 Discuss with the study physician Nephrology consult Monitor creatinine daily Administer corticosteroids at a dose of 1-2 mg/kg/day prednisone equivalents followed by corticosteroid taper for life-threatening (Grade 4) serum creatinine elevation and permanently discontinue. For severe (Grade 3) withhold and administer corticosteroids at a dose of 0.5 to 1 mg/kg/day prednisone equivalents followed by corticosteroid taper. If worsening or no improvement occurs, increase dose of corticosteroids to 1 to 2 mg/kg/day prednisone equivalents and permanently discontinue.
Rash (excluding Bullous skin formations)		
Grade	Dose Modifications	Toxicity Management
Any Grade		Monitor for signs and symptoms of dermatitis (rash and pruritus) **IF THERE IS ANY BULLOUS FORMATION, THE STUDY PHYSICIAN SHOULD BE CONTACTED**
Grade 1	Continue dosing.	Consider symptomatic treatment including oral antipruritics (e.g., diphenhydramine or hydroxyzine) and topical therapy (e.g., urea cream)
Grade 2	
For persistent (> 1- 2 weeks) Grade 2 events, hold scheduled study drug up to 28 days until resolution to ≤ Grade 1 or baseline
 
 If toxicity worsens then treat as Grade 3 If toxicity improves then resume administration at next scheduled dose 	
 Consider symptomatic treatment including oral antipruritics (e.g., diphenhydramine or hydroxyzine) and topical therapy (e.g., urea cream) Consider moderate-strength topical steroid If no improvement of rash/skin lesions occurs within 3-5 days or is worsening, discuss with study physician and consider systemic steroids prednisone 0.5 to 1 mg/kg/day or IV equivalent Consider dermatology consult Consider skin biopsy if persistent for >1-2 weeks or recurs
Grade 3**	
Hold study drug up to 28 days until resolution to ≤ Grade 1 or baseline. If temporarily holding the study drug/study regimen does not provide improvement of the Grade 3 skin rash to ≤ Grade 1 or baseline within 28 days, then permanently discontinue Study drug
	
 Discuss with study physician Consider hospitalization Monitor extent of rash [Rule of Nines] Consult dermatology Consider skin biopsy (preferably more than 
 as clinically feasible. Initiate empiric IV corticosteroids (e.g., methylprednisolone IV or equivalent) at 1 to 2 mg/kg/day Once improving, gradually taper steroids over ≥4 weeks and consider prophylactic antibiotics 
**If SJS/TEN is suspected, withhold I-O therapy and refer patient for specialized care for assessment and treatment. If SJS or TEN

Grade 4**	Permanently discontinue	

study drug/study regimen		is diagnosed, permanently discontinue I-O therapy.
Endocrinopathy (e.g. hyperthyroidism, hypothyroidism, hypopituitarism, adrenal insufficiency, etc.)		
Grade	Dose Modifications	Toxicity Management
Any Grade		
 Monitor subjects for signs and symptoms of endocrinopathies. Non-specific symptoms include headache, fatigue, behavior changes, changed mental status, vertigo, abdominal pain, unusual bowel habits, hypotension and weakness. Subjects should be thoroughly evaluated to rule out any alternative etiology (e.g., disease progression including brain metastases, infections, etc.) Monitor and evaluate thyroid function tests: TSH, free T₃ and free T₄ and other relevant endocrine labs depending on suspected endocrinopathy. If a subject experiences an AE that is thought to be possibly of autoimmune nature (e.g., thyroiditis, pancreatitis, hypophysitis, diabetes insipidus), the investigator should send a blood sample for appropriate autoimmune antibody testing
Grade 1	Continue dosing.	For Grade 1: (including those with asymptomatic TSH elevation) 
 Monitor patient with appropriate endocrine function tests If TSH < 0.5X LLN, or TSH >2X ULN or consistently out of range in 2 subsequent measurements, include FT4 at subsequent cycles as clinically indicated and consider endocrinology consult.
Grade 2	Hold study drug up to 28 days until resolution to ≤ Grade 1 
 If worsens then treat as Grade 3 or Grade 4 If toxicity improves to baseline then treat at next scheduled treatment date 	For Grade 2: (including those with symptomatic endocrinopathy) 
 Discuss with study physician Initiate hormone replacement as needed for management Evaluate endocrine function, and as clinically indicated, consider pituitary scan For subjects with abnormal endocrine work up, consider short-term, high-dose corticosteroids (e.g., methylprednisolone or IV equivalent) with relevant hormone replacement (e.g., levothyroxine, hydrocortisone, or sex hormones) For subjects with normal endocrine work up (lab or MRI scans), repeat labs/MRI as clinically indicated.
Grade 3	Hold study drug up to 28 days until endocrinopathy symptom(s) are controlled. Resume study drug/study regimen administration if controlled at the next scheduled dose.	
 Discuss with study physician Initiate empiric IV corticosteroids (e.g., methylprednisolone IV or equivalent) at 1 to 2 mg/kg/day Administer hormone replacement therapy as necessary For adrenal crisis, severe dehydration, hypotension, or shock: immediately initiate intravenous corticosteroids with mineralocorticoid activity Consult endocrinologist Once improving, gradually taper immunosuppressive steroids over ≥4 weeks
Grade 4	Permanently discontinue study drug/study regimen	
Immune mediated Neurotoxicity (except Myasthenia Gravis and Guillain-Barre)		
Grade	Dose Modifications	Toxicity Management
Any Grade		
 Subjects should be evaluated to rule out any alternative etiology (e.g., disease progression, infections, metabolic syndromes and

		
medications, etc.)
 
 • Monitor subject for general symptoms (headache, nausea, vertigo, behavior change, or weakness) • Consider appropriate diagnostic testing (e.g. electromyogram and nerve conduction investigations) • Symptomatic treatment with neurological consult as appropriate
Grade 1	Continue dosing	
Grade 2	
 • For acute motor neuropathies or neurotoxicity, hold study drug up to 28 days until resolution to ≤ Grade 1 • For sensory neuropathy/neuropathic pain, consider holding study drug up to 28 days until resolution to ≤ Grade 1 or baseline. 
 ○ If toxicity worsens then treat as Grade 3 or Grade 4 ○ If toxicity improves then treat at next scheduled treatment date 	
 • Discuss with the study physician • Consider Neurology Consult • Sensory neuropathy/neuropathic pain may be managed by appropriate medications (e.g., gabapentin, duloxetine, etc.) • Consider systemic steroids prednisone 1- 2mg/kg/day or IV equivalent at 0.5 to 1 mg/kg/day • If no improvement within 3-5 days, consider additional workup and treatment with additional immunosuppressive therapy (e.g. IVIgG)
Grade 3 or higher	Permanently discontinue study drug/study regimen	
 • Discuss with study physician • Consult Neurology Consult • Consider hospitalization • Consider empiric IV corticosteroids (e.g., methylprednisolone or IV equivalent) at 1 to 2 mg/kg/day • If no improvement within 3-5 days, consider additional workup and treatment with additional immunosuppressants (e.g. IVIgG) • Once stable, gradually taper steroids over ≥4 weeks
Immune-mediated peripheral neuromotor syndromes, such as Guillain-Barre and Myasthenia Gravis		
Grade	Dose Modifications	Toxicity Management
Any Grade		
 • The prompt diagnosis of immune-mediated peripheral neuromotor syndromes is important, since certain subjects may unpredictably experience acute decompensations which can result in substantial morbidity or in the worst case, death. Special care should be taken for certain sentinel symptoms which may predict a more severe outcome, such as prominent dysphagia, rapidly progressive weakness, and signs of respiratory insufficiency or autonomic instability

		
 • Subjects should be evaluated to rule out any alternative etiology (e.g., disease progression, infections, metabolic syndromes and medications, etc.). It should be noted that the diagnosis of immune-mediated peripheral neuromotor syndromes can be particularly challenging in subjects with underlying cancer, due to the multiple potential confounding effects of cancer (and its treatments) throughout the neuraxis. 
 ○ Given the importance of prompt and accurate diagnosis, it is essential to have a low threshold to obtain a neurological consult • Neurophysiologic diagnostic testing (e.g., electromyogram and nerve conduction investigations, and “repetitive stimulation” if myasthenia is suspected) are routinely indicated upon suspicion of such conditions and may be best facilitated by means of a neurology consultation • Important to consider that the use of steroids as the primary treatment of Guillain-Barre is not typically considered effective. Subjects requiring treatment should be considered for plasmapheresis (or IVIgG, as an alternative)
Grade 1	Continue dosing.	
 • Discuss with the study physician • Care should be taken to monitor subjects for sentinel symptoms of a potential decompensation as described above • Consider a neurology consult unless the symptoms are very minor and stable
Grade 2	
Hold study drug up to 28 days until resolution to ≤ Grade 1 or baseline
 
Permanently discontinue study drug if it does not resolve to ≤ Grade 1 within 28 days or if there are signs of respiratory insufficiency or autonomic instability
	
Grade 2 : Moderate
 
 • Discuss with the study physician • Care should be taken to monitor subjects for sentinel symptoms of a potential decompensation as described above • Obtain a Neurology Consult • Sensory neuropathy/neuropathic pain may be managed by appropriate medications (e.g., gabapentin, duloxetine, etc.) 
MYASTHENIA GRAVIS
 
 ○ Steroids may be successfully used to treat Myasthenia Gravis. Important to consider that steroid therapy (especially with high doses) may result in transient worsening of myasthenia and should typically be administered in a monitored setting under supervision of a consulting neurologist. ○ Subjects unable to tolerate steroids may be candidates for treatment with plasmapheresis or IVIgG. Such decisions are best made in consultation with a neurologist, taking into account the unique needs of each patient. ○ If Myasthenia Gravis-like neurotoxicity present, consider starting acetylcholine esterase ¹⁷ inhibitor therapy in addition to steroids. Such therapy, if successful, can also serve to reinforce the diagnosis. 
GUILLAIN-BARRE:
 
 ○ Important to consider here that the use of steroids as the primary treatment of Guillain-Barre is not typically considered effective.

		
 Subjects requiring treatment should be considered for plasmapheresis (or IVIg, as an alternative).
Grade 3 or higher	Permanently discontinue study drug/study regimen.	
For severe or life threatening (Grade 3 or 4) events:
 
 - Discuss with study physician - Recommend hospitalization - Monitor symptoms and obtain neurological consult 
MYASTHENIA GRAVIS
 
 o Steroids may be successfully used to treat Myasthenia Gravis. It should typically be administered in a monitored setting under supervision of a consulting neurologist. o Subjects unable to tolerate steroids may be candidates for treatment with plasmapheresis or IVIg. o If Myasthenia Gravis-like neurotoxicity present, consider starting acetylcholine esterase¹⁷ inhibitor therapy in addition to steroids. Such therapy, if successful, can also serve to reinforce the diagnosis. 
GUILLAIN-BARRE:
 
 o Important to consider here that the use of steroids as the primary treatment of Guillain-Barre is not typically considered effective. 
Subjects requiring treatment should be considered for plasmapheresis (or IVIg, as an alternative).

Infusion-related reactions

Grade	Dose Modifications	Toxicity Management
Any Grade		
 Management per institutional standard at the discretion of investigator Monitor subjects for signs and symptoms of infusion-related reactions (e.g., fever and/or shaking chills, flushing and/or itching, alterations in heart rate and blood pressure, dyspnea or chest discomfort, skin rashes etc.) and anaphylaxis (e.g., generalized urticaria, angioedema, wheezing, hypotension, tachycardia, etc.)
Grade 1	The infusion rate of study drug/study regimen may be decreased by 50% or temporarily interrupted until resolution of the event	
 Acetaminophen and/or antihistamines may be administered per institutional standard at the discretion of the investigator Consider premedication per institutional standard prior to subsequent doses
Grade 2	The infusion rate of study drug/study regimen may be decreased 50% or temporarily interrupted until resolution of the event (up to 4 hours) Subsequent infusions may be	

	given at 50% of the initial infusion rate	
Grade 3 or 4	Permanently discontinue study drug/study regimen.	Manage severe infusion- related reactions per institutional standards (e.g., IM epinephrine, followed by IV diphenhydramine and ranitidine, and IV glucocorticoid)
Non- immune Mediated Reactions		
Grade	Dose Modifications	Toxicity Management
Any Grade	Note: dose modifications are not required for adverse events not deemed to be related to study treatment (i.e. events due to underlying disease) or for laboratory abnormalities not deemed to be clinically significant.	Treat accordingly as per institutional standard.
1	No dose adjustment.	Treat accordingly as per institutional standard
2	Hold study drug up to 28 days until resolution to ≤ Grade 1 or baseline	Treat accordingly as per institutional standard
3	Hold study drug up to 28 days until resolution to ≤ Grade 1 or baseline For AEs that downgrade to ≤ Grade 2 within 7 days AND resolve to ≤ Grade 1 or baseline within 14 days, resume study drug/study regimen administration at next scheduled dose. Otherwise, discontinue study drug/study regimen	Treat accordingly as per institutional standard
4	Discontinue Study drug/study regimen (Note for Grade 4 labs, decision to discontinue would be based on accompanying clinical signs/symptoms	Treat accordingly as per institutional standard

	and as per Investigator’s clinical judgment and in consultation with the sponsor)	
--	---	--

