Absolute Neutrophil Count	1 ≥1.5 x 10 ⁹ /L	No dose adjustment required
	2 ≥1.0 - <1.5 x 10 ⁹ /L	No dose adjustment required
	3 ≥0.5 - <1.0 x 10 ⁹ /L	Dose interruption for up to 28 days until recovery to ≥1.0 x 10 ⁹ /L. Re-initiate veliparib at the same dose level. If toxicity recurs at Grade 3: temporary dose interruption until recovery to > 1.0 x 10 ⁹ /L and reduce veliparib to the next lower dose level.
	4 <0.5 x 10 ⁹ /L	Dose interruption for up to 28 days until recovery to ≥1.0 x 10 ⁹ /L. Re-initiate veliparib at the same dose level. If toxicity recurs at Grade 4: temporary dose interruption until recovery to > 1.0 x 10 ⁹ /L and reduce veliparib to the next lower dose level.
Lymphopenia	1 ≥800/mm ³	No dose adjustment required
	2 ≥500 - <800/mm ³	No dose adjustment required
	3 ≥200 - <500/mm ³	Dose interruption for up to 28 days until recovery to Grade ≤ 1. Re-initiate veliparib at the next lower dose level. If toxicity recurs at Grade 3: temporary dose interruption until recovery to Grade ≤ 1 and reduce veliparib to the next lower dose level.
	4 <200/mm ³	Dose interruption for up to 28 days until recovery to grade ≤ 1. Re-initiate veliparib at the next lower dose level. If toxicity recurs at grade 4: discontinue veliparib.
Non-Hematologic Toxicities		
Myelodysplastic syndrome/Acute Myeloid Leukemia		Discontinue veliparib
Pneumonitis		Discontinue veliparib
Embryo-Fetal Toxicity		If patient becomes pregnant, discuss with the patient the potential hazard to the fetus.
Nausea	
5-HT3 antagonists (ondansetron, granisetron, palonosetron), dopamine antagonists (prochlorperazine, metoclopramide) and lorazepam were most frequently used to manage veliparib-associated nausea. Anti-emetics should be initially prescribed on a specified schedule (e.g., no PRN). Multiple concomitant anti-emetic medications may be needed in some cases for effective nausea management. Example regimens and combinations to consider include:
 
 ○ Ondansetron 4 or 8 mg BID ○ Lorazepam 0.5 mg Q8H ○ Ondansetron 8 MG Q8H; prochlorperazine 10 MG Q6H ○ Lorazepam 1 mg Q8H; prochlorperazine 10 mg Q6H; ondansetron 8 mg Q8H ○ Lorazepam 1 mg Q8H; ondansetron 8 mg Q8H; omeprazole 20 mg QD 	

Toxicity	Grade	Dose Adjustment and Management Recommendations

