APPENDIX D – ADVERSE EVENT ALGORITHMS

Recommended management algorithms for suspected nivolumab related endocrinopathy, gastrointestinal toxicity, hepatotoxicity, neurologic toxicity, pulmonary toxicity, renal toxicity and skin toxicity.

Endocrinopathy Management Algorithm

[figure not shown]
Rule out non-inflammatory causes. If non-inflammatory cause, treat accordingly and continue I-O therapy. Consider visual field testing, endocrinology consultation, and imaging.

Patients on IV steroids may be switched to an equivalent dose of oral corticosteroids (e.g. prednisone) at start of tapering or earlier, once sustained clinical improvement is observed. Lower bioavailability of oral corticosteroids should be taken into account when switching to the equivalent dose of oral corticosteroids.

GI Adverse Event Management Algorithm

[figure not shown]
Rule out non-inflammatory causes. If non-inflammatory cause is identified, treat accordingly and continue I-O therapy. Opiates/narcotics may mask symptoms of perforation. Infliximab should not be used in cases of perforation or sepsis.

Patients on IV steroids may be switched to an equivalent dose of oral corticosteroids (e.g. prednisone) at start of tapering or earlier, once sustained clinical improvement is observed. Lower bioavailability of oral corticosteroids should be taken into account when switching to the equivalent dose of oral corticosteroids.

Hepatic Adverse Event Management Algorithm

Rule out non-inflammatory causes. If non-inflammatory cause, treat accordingly and continue I-O therapy. Consider imaging for obstruction.

[figure not shown]
Patients on IV steroids may be switched to an equivalent dose of oral corticosteroids (e.g. prednisone) at start of tapering or earlier, once sustained clinical improvement is observed. Lower bioavailability of oral corticosteroids should be taken into account when switching to the equivalent dose of oral corticosteroids.

*I-O therapy may be delayed rather than discontinued if AST/ALT ≤ 8 x ULN or T.bili ≤ 5 x ULN.

**The recommended starting dose for grade 4 hepatitis is 2 mg/kg/day methylprednisolone IV.

Neurological Adverse Event Management Algorithm

[figure not shown]
Rule out non-inflammatory causes. If non-inflammatory cause, treat accordingly and continue I-O therapy.

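### Table 4.6 gives inconsistent steroid instructions for Grade 2 neurotoxicity and Grade 2 pneumonitis, and Tables 4.5 and 4.6 are not reconciled for Grade 1-2 pneumonitis of uncertain attribution

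*Combined protocol and SAP*

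**What the plan says.** **Grade 2 neurotoxicity (Table 4.6, immune-mediated neurotoxicity other than myasthenia gravis and Guillain-Barre).** A single line reads "Consider systemic steroids prednisone 1- 2mg/kg/day or IV equivalent at 0.5 to 1 mg/kg/day".

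**Grade 2 pneumonitis (Table 4.6).** The first steroid instruction is to "consider systemic steroids (e.g., prednisone 1- 2mg/kg/day or IV equivalent". The later one is "If no improvement within 3-5 days, additional workup and treatment with IV methylprednisolone 1mg/kg/day should be considered". The line after that moves to further immunosuppression.

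**Pneumonitis and veliparib.** In Table 4.5 (section 4.5.1) the pneumonitis row has no grade, and its whole entry is to "discontinue veliparib". In Table 4.6 the Grade 1 entry is "No dose hold required. However, consider holding study drug/study regimen dosing as clinically appropriate", with the diagnostic work-up given as one occasion for a hold. At Grade 2 the study drug is held for up to 28 days, and treatment resumes at the next scheduled date if the event improves. At Grade 3 or 4 the stop is permanent.

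**Which table applies.** Section 4.4 limits dose modification to toxicity attributed to the respective drug. Where attribution is uncertain or toxicities overlap, it says both drugs are to be held and/or modified under the guidelines.

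**The concern.** These are safety instructions that a treating physician follows at the bedside. In the neurotoxicity row, two physicians can use the same line and give doses about twofold apart, each believing the dose to be the stated equivalent of the other. In the pneumonitis row, a patient who is not improving can be moved to a dose no higher than the one already given, and lower if the start was near the top of the range. For a Grade 1 or 2 pneumonitis that cannot be attributed to one drug, one reader may end veliparib permanently while another continues or resumes it. Exposure and reasons for discontinuation would then depend on which table was opened first.

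**Working it through.** No sample size, power or error rate depends on this point. The check compares the printed cells and takes ratios of the printed doses.

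**Assumption.** The documents give no conversion between methylprednisolone and prednisone; Appendix D only cautions that oral bioavailability is lower. Let *f* be the prednisone equivalent of 1 mg IV methylprednisolone. It is taken over an assumed range from 1.0 (face value) to 1.25. In the neurotoxicity row the IV drug is not named, so applying *f* there also assumes methylprednisolone.

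**1. Neurotoxicity Grade 2.** Oral range 1-2 mg/kg/day, IV range 0.5-1 mg/kg/day. Ratio = oral / (IV × *f*).

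| *f* | Low end | High end |
|---|---|---|
| 1.0 | 1 / 0.5 = 2.0 | 2 / 1 = 2.0 |
| 1.25 | 1 / 0.625 = 1.6 | 2 / 1.25 = 1.6 |

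The two ranges coincide only if *f* = 2, which is outside the assumed range.

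**2. Pneumonitis Grade 2.** Start 1-2 mg/kg/day prednisone or IV equivalent; step 1 mg/kg/day IV methylprednisolone. Step in prednisone terms = 1 × *f*.

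| *f* | Step | Step / bottom of start | Step / top of start | Starts that the step exceeds |
|---|---|---|---|---|
| 1.0 | 1.00 | 1.0 | 0.5 | none |
| 1.25 | 1.25 | 1.25 | 0.625 | 1.00 to below 1.25 |

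At *f* = 1.25 the step is not above any start from 1.25 to 2, which is (2 − 1.25) / (2 − 1) = 75% of the printed range.

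Other Grade 2 rows of the same table rise at the corresponding point. Diarrhea begins at 0.5-1 mg/kg/day and later reaches "additional workup and treatment with IV methylprednisolone 1-2mg/kg/day should be considered". Hepatitis goes from 0.5-1 to 2-4 mg/kg/day. The pneumonitis row therefore departs from the table's own pattern. This does not show which of its two entries is the wrong one.

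**3. Pneumonitis, Table 4.5 against Table 4.6, when section 4.4 brings in both.**

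| Grade | Table 4.5 (veliparib) | Table 4.6 | Compatible? |
|---|---|---|---|
| 1 | discontinue (no grade given) | no hold required, hold optional | not if Table 4.6 covers veliparib |
| 2 | discontinue (no grade given) | hold, then resume on improvement | not if Table 4.6 covers veliparib |
| 3-4 | discontinue (no grade given) | permanent stop | yes |

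The answer for Grades 1 and 2 turns on what Table 4.6 means by its drug terms. It uses 'study drug' in the Grade 2 cell and 'study drug/study regimen' in the others, and does not say whether either includes veliparib. If both mean nivolumab alone, the tables can be applied side by side. If they include veliparib, the same event has two instructions.

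**The case against.** **On the steroid rows.** The doses are advisory: the wording is to consider them, some as examples. The pneumonitis comparison sets prednisone against methylprednisolone without a stated conversion, and the step may be meant as a change from oral to IV. Part of this stands. With an assumed factor up to 1.25 the step does exceed the lowest quarter of the starting range, and a step-down arises only for a patient started higher up. The route argument is weaker, because the starting instruction already allows an IV equivalent. None of it resolves the neurotoxicity line, where one instruction calls two different ranges equivalent.

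**On Tables 4.5 and 4.6.** A reader might infer that Table 4.5 stops veliparib wherever Table 4.6 continues the regimen. The documents do not support that. The tables are titled by drug, section 4.4 separates them by attribution, and the pneumonitis heading in Table 4.6 asks the treating physician to determine attribution. Table 4.6 also holds at Grade 2 and stops at Grades 3 and 4. What remains is Grade 1 or 2 with uncertain or shared attribution.

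**On hepatitis.** A reader might add the hepatitis steroid doses to the list, because Table 4.6 says for Grade 3 or higher "Initiate empiric IV corticosteroids (e.g., methylprednisolone IV or equivalent) at 1 to 4 mg/kg/day" while Appendix D states "The recommended starting dose for grade 4 hepatitis is 2 mg/kg/day methylprednisolone IV". A single value for Grade 4 that lies inside the wider 1-4 range does not contradict it. The 2-4 mg/kg/day in the Grade 2 row is a later step, after 0.5-1 mg/kg/day has failed, so it is not comparable with a Grade 3 starting dose.

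**On efficacy.** A reader might also infer an effect on the 8-week response rate. The documents give no pneumonitis rate for this combination. Stopping veliparib does not by itself stop nivolumab or remove a patient from the response analysis. No such effect can be shown.

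**Conclusion.** The point holds for three specific places.

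- The Grade 2 neurotoxicity line is inconsistent as printed: a factor of 2 at face value and 1.6 at an assumed conversion of 1.25. It is one row, not a general feature of the tables.
- The Grade 2 pneumonitis step is not above its starting range at face value. Under the assumed 1.25 it exceeds only starts below 1.25 mg/kg/day. This rests on a conversion that the documents do not define.
- Tables 4.5 and 4.6 leave the handling of veliparib open for Grade 1-2 pneumonitis of uncertain or shared attribution. The cause is an ungraded row in one table and an undefined term in the other. At Grades 3 and 4 the tables agree.

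The consequence is ambiguity in safety management. No operating characteristic of the trial changes.

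**What to change.** - Reconcile the two ranges in the Grade 2 neurotoxicity cell of Table 4.6, so that the line carries one consistent instruction.
- Reconcile the starting and non-response instructions in the Grade 2 pneumonitis cell. If equivalence between drugs or routes is relied on, state the conversion.
- Reconcile the pneumonitis rows of Tables 4.5 and 4.6 with the attribution rule in section 4.4: say which grades the Table 4.5 row covers, and what happens to each drug when attribution is uncertain or shared.
- Define 'study drug' and 'study drug/study regimen' in Table 4.6, making clear whether they include veliparib.

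The clinical team decides which values and rules stand; this review does not propose any. The cost is amendment wording in Tables 4.5 and 4.6. The design, sample size and analysis are unaffected.
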